Study protocol

Ultrasound-assisted vs. real-time ultrasound-guided paracentral approach combined lumbar and epidural anesthesia in elderly patients: a randomized controlled study

Version: 2.0

Version Date: 2024/2/1

1. Research background

Traditional body surface marker guided intraspinal anesthesia can meet most of the clinical anesthesia needs, but for the presence of obesity, spinal deformity, senile ligament calcification, previous lumbar surgery history, etc., intraspinal puncture often has technical difficulties. Ultrasound-guided intraspinal puncture can provide anatomical information related to the puncture site, including intervertebral segment, posterior median line of the spine, vertebral canal depth, and distribution characteristics of each ligament, providing a solution for difficult puncture and improving the accuracy and safety of intraspinal puncture 1,2.

During the implementation of lumbar anesthesia, multiple punctures through ligaments and dura can easily lead to postoperative headache, low back pain, and may increase the incidence of paresthesia and spinal cord hematoma. Ultrasonic-guided spinal anesthesia can reduce the number of passages required to enter the subarachnoid space compared with the traditional signpost guided midline approach. Ultrasound examination before hip and knee replacement provides guidance for intraspinal puncture, which can significantly reduce the number of entry into the subarachnoid space and the number of attempts3. In addition, a pre-ultrasound scan of the spine before puncture can estimate the distance from the skin to the epidural space and determine the appropriate puncture point, which is important in obese women (BMI: 33~86 kg/m²) epidural labor analgesia is especially effective when the epidural needle is placed at the intended puncture point, 76.1% of women did not change the point of re-puncture, 67.4% of women did not redirection4. However, despite the ability of ultrasound to provide anatomical information about the spine, 23 (10.7%) of 218 women in a study had misidentification of 2 or more intervertebral spaces, which increases the risk of intraseptic puncture complications. Subgroup analysis showed that the degree of access to the maternal spinous process had an impact on the recognition of the lumbar space in spinal ultrasound. Women with easy access to the spinous process have a higher success rate of ultrasound-assisted first puncture 5. Based on the posterior longitudinal ligament ultrasonic image scoring system, Weed JT et al. 's study showed that the puncture frequency and puncture time were significantly reduced in the group with a high rating of clear images, suggesting that the calcification level of the posterior longitudinal ligament may be one of the important factors affecting the success rate of ultrasound-guided intra spinal puncture through the posterior median approach.

It can be seen from the above description that ultrasound assisted positioning before intraspinal anesthesia has more technical advantages than body surface marking, but at the same time, the puncture process of the above two methods is still a "blind exploration" operation with or without anatomical preview, and the puncture path is easily blocked by vertebrae and its accessory structures, and the puncture Angle is not visible. Real-time ultrasound guidance can solve the problem of path selection in difficult puncture. Therefore, Lee, P. J., et al. developed a technique for real-time ultrasound guidance of intraspinal anesthesia via the Taylor approach (auxiliary approach in the L5-S1 space) by conducting a preliminary cadential study on 5 unembalmed cadasses. Subsequently, 10 patients undergoing joint replacement underwent successful hip arthroplasty using real-time ultrasound-guided intraspinal anesthesia in prone position. Subsequently, Chong, S. E. et al. compared real-time ultrasound guided (UG) and body surface marking touch (PG), and the results showed that the success rate of the first puncture in the UG group (≤ 6 skin piercings with or without redirection) was significantly higher than that in the PG group (87% vs. 43%, $P<0.001$). UG also had a higher success rate of single needle passage (47% vs. 20%, $p = 0.028$). The mean (SD) time to success of dural puncture was shorter in UG group [0.69(1.01) and 1.60 (1.19)min, $P=0.002$]. This is comparable to the results of the Conroy9 study, which showed a time of 1.2 minutes (0.2-15 minutes). It can be seen that both real-time ultrasound-guided intraspinal anesthesia and preoperative ultrasound-assisted intraspinal anesthesia have certain technical advantages compared with body surface labeling.

The ultrasound imaging along the longitudinal median path of the spine has less bone and ligament occlusion, and the intravertebral canal image is often clearer, which is better than the transverse or longitudinal scan of the posterior median line. Therefore, the real-time ultrasound guidance technology should adopt the paramedical approach. Chen L et al. conducted a comparison of the effects of ultrasound assisted positioning (USAS) and real-time ultrasound guidance (USRTG) in intra spinal anesthesia. In a study of 114 elderly hip fracture patients (≥ 70 years), they found that the USAS group had a higher success rate on the first attempt (successful dural puncture without redirection) (80.7% vs 52.6%) and a higher success rate on the first pass (63.2% vs 31.6%). Fewer attempts (skin piercings) (1 [1-1]vs 1 [1-3]) and median pass rates were significantly lower in the USAS group than in the USRTG group. However, the USRTG group had a shorter positioning time (175 s [129-234 s]vs 315 s [250-390 s]).

However, the operation time was longer (488 seconds [260-972 seconds]vs 200 seconds [127-328 seconds]) and the total time was longer (694 seconds [421-1133 seconds]vs 540 seconds [432-641 seconds]). The USAS group had higher satisfaction scores. Overall, anesthesiologists rated the USRTG group as "more difficult." Chen L and his colleagues believe that in elderly patients with hip fractures, USRTG technique is not superior to USAS technique for lumbar anesthesia, because USRTG technique has a lower success rate, longer operation time, lower satisfaction score, and greater difficulty in operation. Therefore, USAS technology may be more suitable for elderly patients.

Both continuous epidural anesthesia (CSA) and lumbar anesthesia (SA) can be used in elderly patients undergoing hip fracture surgery. Based on a study of 74 elderly hip fractures. In the SA group, 68 percent of patients experienced at least one episode of hypotension (a decrease in systolic blood pressure greater than 20 percent of baseline values), compared to 31 percent of patients in the CSA group. In the SA group, 51 percent of patients experienced at least one episode of severe hypotension (a drop in systolic blood pressure greater than 30 percent of baseline value), compared to only 8 percent of patients in the CSA group. Patients in the SA group required more ephedrine doses. Therefore, the authors suggest that CSA may reduce the onset of hypotension and severe hypotension¹². Through A review by Perlas A et al., we found data from eight studies showing that ultrasound can identify a given lumbar space more accurately than palpation alone. Thirteen studies reported a good correlation between depth measured by ultrasound and needle insertion depth in the epidural or intravaginal space, with the average difference between the two measurements within 3 mm in most studies. Spinal canal ultrasound increased the success rate of puncture and reduced the difficulty of puncture ¹.

According to the clinical experience of our center in using ultrasound to guide intraspinal operation, we believe that skilled use of ultrasound is also an important factor affecting the success rate of the first intraspinal puncture and shortening the puncture time, and the conclusion may be different from Chen L et al. Therefore, we designed this study to explore the difference in clinical effects between the application of ultrasound-assisted positioning by experienced operators and real-time ultrasound-guided paramedical approach combined lumbar and epidural anesthesia in elderly patients, providing validation for the clinical use and promotion of real-time intraspinal ultrasound technology.

2. Research purpose

The purpose of this study was to investigate the difference of clinical effect between ultrasound-assisted positioning and real-time ultrasound-guided paracentral combined epidural anesthesia in elderly patients.

3. Study design

This was a prospective randomized controlled study.

3.1 Patient selection and allocation.

3.1.1 sample size calculating

This study is intended to include all patients who will undergo combined spinal and epidural anesthesia from October 2023 to October 2024. Adopt PASS V21.0.3 software (2021; NCSS LLC) calculated the study sample size. According to a preliminary study by Chen L et al., the success rate of the first puncture using the USAS technique and the USRTG technique was 80.7% vs 52.6%, respectively. It was calculated that 43 patients were required in each group at a bilateral significance level of 0.05 ($\alpha = 0.05$) and 80% efficacy ($\beta = 0.2$). Taking into account 10% of possible patients dropping out, the sample size was increased to 48 patients per group for a total of 96 patients.

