of paracentral sagittal section (IPP)) were recorded, and the optimal puncture section considered by the operator (the widest acoustic window at the back of the complex) was selected to record the best gap, puncture Angle and depth. In the sterile state, traditional blind operation was performed; The positioning time, the depth and width of the retrodural complex, the first successful attempt (first skin piercing without redirection), the number of skin piercings, the number of redirects, and the operation time (probe touching the skin until the end of the operation) were recorded. After successful epidural puncture, 25G lumbar anesthesia needle was inserted (if CSF outflow was not smooth, the epidural needle could be rotated in place and then re-inserted into the epidural puncture). Subarachnoid block (2.5mL/12.5mg of 0.5% ropivacaine without high glucose) was performed immediately after CSF outflow was smooth, followed by epidural catheter. If there is no CSF after withdrawal, skin puncture should be performed again. The maximum number of skin puncture should be 6 times, and the cumulative redirection of each skin puncture should not exceed 6 times. If six skin piercings are unsuccessful, traditional palpation, replacement of puncture Spaces, or general anesthesia are considered and recorded.

In the US-RTG group, the optimal puncture section considered by the operator was selected and recorded directly in the plane of the paracentral transverse section, out of the plane of the paracentral sagittal section or in the plane of the paracentral sagittal section for real-time ultrasound guided lumbar epidural anesthesia. The positioning time, the depth and width of the retrodural complex, the first successful attempt (first skin piercing without redirection), the number of skin piercings, the number of redirects, and the operation time (probe touching the skin until the end of the operation) were recorded. After successful epidural puncture, 25G lumbar anesthesia needle was inserted (if CSF outflow was not smooth, the epidural needle could be rotated in place and then re-inserted into the epidural puncture). Subarachnoid block (2.5mL/12.5mg of 0.5% ropivacaine without high glucose) was performed immediately after CSF outflow was smooth, followed by epidural catheter. If there is no CSF after withdrawal, skin puncture should be performed again.

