The maximum number of skin puncture should be 6 times, and the cumulative redirection of each skin puncture should not exceed 6 times. If six skin piercings are unsuccessful, traditional palpation, replacement of puncture Spaces, or general anesthesia are considered and recorded.

Whether the patient was in the left or right decubitus position, the operator used the puncture needle manually and the ultrasound probe non-manually. Adverse reactions and complications were recorded in both groups, including radicular pain, bloody cerebrospinal fluid puncture, headache after dural puncture, paresthesia, back pain, whether traditional palpation was used, the puncture space was changed, or general anesthesia was used. Patient satisfaction score: Patients were asked to use a 5-point numerical rating scale to evaluate their satisfaction (1, very dissatisfied; 5, very satisfied). The VNRS, verbal numerical rating scale (0-10) and whether to add analgesic drugs were recorded in the two groups.

3. Outcomes

Primary outcomes: first attempt success rate (first skin piercing, no redirection);

Secondary outcomes: operation time (seconds), positioning time, depth and width of posterior dural complex, skin puncture number, redirection number;

Patient satisfaction score: Patients were asked to use a 5-point numerical rating scale to evaluate their satisfaction (1, very dissatisfied; 5, very satisfied).

Operation difficulty score: After the operation, the anesthesiologist will score the difficulty of this operation (1, very dissatisfied; 5, very satisfied). Change of anesthesia method (traditional blind method, USAS or USRTG, change of puncture space, general anesthesia).

Adverse reactions and complications: include radicular pain, bleeding, puncture, headache after dural puncture, paraesthesia, and back pain.

Reference

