## Statistical analysis

All statistical analysis were performed using Statistical Package for Social Sciences (SPSS) for Windows software version 23. Numerical variables were expressed as mean  $\pm$  SD or median (minimum–maximum). Categorical variables were expressed as frequency (%). Test of normality was done using Kolmogorov–Smirnov test. One-Way analysis of variance (ANOVA) was used to compare means if data distribution was normal, or nonparametric test Mann-Whitney U was used if data was not distributed normally. Pearson chi-square or Fischer's exact test was used for assessing categorical variables. Log rank test was used to evaluate the time difference in the first administration of diclofenac sodium after surgery, and hazard ratio (HR) was used to evaluate the benefit. All tests were two-tailed, and the significance level was set at  $\alpha$  0.05.

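### Does the background's pair of success rates from the source trial undermine the planning figures in section 3.1.1?

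*Protocol*

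**What the plan says.** Protocol section 1 summarises an earlier randomised trial of the same two techniques: "In a study of 114 elderly hip fracture patients". It gives ultrasound-assisted vs real-time-guided results as "successful dural puncture without redirection) (80.7% vs 52.6%) and a higher success rate on the first pass (63.2% vs 31.6" percent. The following sentence equates attempts with skin piercings and mentions passes as a separate quantity: "Fewer attempts (skin piercings) (1 [1-1]vs 1 [1-3]) and median pass rates were significantly lower in the USAS group". A pass is not defined.

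Section 3.1.1 takes the first pair for planning: "the success rate of the first puncture using the USAS technique and the USRTG technique was 80.7% vs 52.6%, respectively". With two-sided alpha 0.05 and 80% power it arrives at 43 per group, raised to 48 per group (96 in total) for 10% dropout.

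The Outcomes item of section 4 defines the primary outcome as "first attempt success rate (first skin piercing, no redirection". Under Statistical analysis, the SAP plans Pearson's chi-square or the alternative ("exact test was used for assessing categorical variables").

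Section 1 closes by giving operator skill as the reason for a new trial: it is "an important factor affecting the success rate of the first intraspinal puncture and shortening the puncture time, and the conclusion may be different from" that of the source trial.

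**The concern.** A needle that reaches its target at the first skin piercing with no redirection has, in ordinary usage, reached it on the first pass. The rate of success without redirection should therefore not exceed the first-pass rate, yet here it does in both arms, by a wide margin. The Protocol's other usage points the same way. Section 1 reports, for another study, success with or without redirection (87% vs 43%) separately from success with a single needle passage (47% vs 20%), and the passage rates are the lower ones.

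The natural suspicion is that 80.7% vs 52.6% is really success at the first skin piercing with redirection allowed, and that 63.2% vs 31.6% is the pair matching this trial's primary outcome. If so, section 3.1.1 would have been planned on a more lenient endpoint than the one to be analysed. That could leave the trial the wrong size, or leave readers judging the new real-time rate against the wrong benchmark (52.6% rather than 31.6%).

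**Working it through.** **1. Size of the apparent inconsistency.** The split of the 114 source patients is not stated. Of splits with between 30 and 84 patients in one arm, only 57 + 57 reproduces all four percentages:

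- assisted: 46/57 = 80.7% and 36/57 = 63.2%
- real-time: 30/57 = 52.6% and 18/57 = 31.6%

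If a pass is one needle advance (an assumption), at least 46 − 36 = 10 assisted patients (17.5 points) and 30 − 18 = 12 real-time patients (21.1 points) are counted in a way that does not fit the labels.

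**2. Reproducing the plan's sample size.** Pooled-variance z formula without continuity correction, with p̄ the mean of the two rates:

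n = [1.960·√(2p̄(1−p̄)) + 0.842·√(p1(1−p1) + p2(1−p2))]² / (p1 − p2)²

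With 0.807 and 0.526, p̄ = 0.6665: n = (1.3068 + 0.5357)² / 0.281² = 3.3947 / 0.07896 = 42.99, so 43. Then 43 / 0.90 = 47.8, so 48 per group and 96 in total. The plan's figures reproduce.

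**3. The same formula with the other pair.** With 0.632 and 0.316, p̄ = 0.474: n = (1.3840 + 0.5638)² / 0.316² = 3.7939 / 0.09986 = 37.99, so 38. Then 38 / 0.90 = 42.2, so 43 per group and 86 in total. The plan already has 96.

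**4. Power under each pair.**

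| Rates | Evaluable per group | Normal approximation | Pearson, exact enumeration | Fisher, exact enumeration |
|---|---|---|---|---|
| 80.7% vs 52.6% | 43 | 80.0% | 81.2% | 74.5% |
| 80.7% vs 52.6% | 48 | 84.3% | 85.0% | 78.6% |
| 63.2% vs 31.6% | 43 | 84.8% | 84.2% | 77.6% |
| 63.2% vs 31.6% | 48 | 88.5% | 88.8% | 84.3% |

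By every method, power at a given n is higher with the first-pass pair. If the label were wrong, the trial would be slightly larger than its own target needs. The lower power of Fisher's test applies to both pairs and is a separate matter from the label.

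**5. Does the benchmark matter?** Suppose 48 evaluable real-time patients. Treating 31.6% and 52.6% as fixed values, a 95% Wilson interval excludes the first and includes the second for 22 to 32 successes (22/48: 32.6% to 59.7%; 32/48: 52.5% to 78.3%). But each source rate comes from only 57 patients. Comparing k/48 with 18/57 and with 30/57 by two-sided Fisher's exact test, the counts that differ from the first and not from the second are 25 to 34 (k = 24: p = 0.072 against 18/57; k = 25: p = 0.046; k = 34: p = 0.072 against 30/57; k = 35: p = 0.044). So there are results whose reading would depend on the label, but only in a comparison across trials that neither document plans.

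**6. The text as it stands.** The background labels the 80.7% vs 52.6% pair as without redirection, section 3.1.1 uses that pair, and the primary outcome excludes redirection. The three places agree. The doubt comes entirely from the second pair and its undefined term.

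**The case for a change.** The strongest argument for acting is that a planning rate should describe the same event as the primary outcome, and here a reader cannot be sure that it does. Section 3.1.1 speaks only of success at first puncture, a phrase section 1 elsewhere attaches to up to six piercings with or without redirection. The trial is also justified by the expectation that skilled operators will change the picture, so which source rate counts as the no-redirection rate affects how the real-time arm is discussed. Checking the source and correcting one label would cost almost nothing.

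Much of this stands as a comment on the background text: on the ordinary meaning of a pass, the two labels do not fit together. It does not carry over to the plan. The source conclusion that this trial might overturn is one between arms, namely that real-time guidance is not superior to ultrasound assistance, and the randomised comparison tests that whichever label is right. An absolute comparison with the source would in any case mix different populations and procedures: hip-fracture patients aged 70 or over having spinal anesthesia there; patients aged 60 or over having combined spinal-epidural anesthesia, with experienced operators, here.

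A related query is whether the permitted manoeuvre in section 4, where "the epidural needle could be rotated in place and then re-inserted into the epidural puncture", counts as a redirection. That is a scoring detail which does not follow from the source-rate question. The manoeuvre is worded identically for both groups, and one convention applied to both arms settles it.

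**Conclusion.** The oddity in section 1 is real on the ordinary meaning of a pass: at least 10 of 57 and 12 of 57 source patients do not fit the labels, assuming 57 per arm and one needle advance per pass. Because the term is undefined, it is an apparent inconsistency and not a proven one, and the documents alone cannot resolve it. Section 3.1.1 is not shown to be wrong. Its arithmetic reproduces, and its input matches the primary outcome as labelled.

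No decision in the plan turns on the answer. The formula asks for 43 per group under one reading and 38 under the other, against 48 planned, assuming the source rates carry over to this population. The outcome definition, the test and the between-arm estimate are unaffected. Authors who later cite the source trial would naturally check its definitions when doing so. This is a wording query in a literature summary, and no change to the plan follows.

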3.1.2 Inclusion criteria

- 1) Elderly patients (≥ 60 years old);
- 2) ASA Grade I to III.

3.1.3 Exclusion criteria

- 1) Severe obesity ($BMI > 35 \text{ kg/m}^2$);
- 2) Spinal deformity or surgical history;
- 3) Allergic to local anesthetics;
- 4) There are coagulation disorders;
- 5) Communication barriers

4. Research process

1. Preoperative records

Patients were visited according to clinical routine on the day before surgery, and their age, gender, height, weight, ASA grade, and operation name were recorded. Patients were identified according to inclusion and exclusion criteria, informed consent was signed, and basic patient information was recorded.

2. Anesthesia protocol and intraoperative records

Based on a computer-generated table of random numbers, they were randomly assigned to receive combined lumbar and epidural anesthesia in either the US-AS group (n=48) or the US-RTG group (n=48). Patient assignments are hidden by sequentially numbered and sealed opaque envelopes that can only be opened by the attending anesthesiologist when the patient enters the operating room. Patients know nothing about grouping. Neither the intraoperative parameter collector nor the anesthesiologist performing the procedure can blind the groups.

All ultrasound-guided CSEA blocks were performed by an attending anesthesiologist (>100 cases per year) who was skilled in ultrasound-assisted and real-time ultrasound-guided intra spinal block, and another attending physician who was familiar with the procedure was responsible for parameter recording. When the patient enters the room, connect the monitor. Nasal catheter oxygen (oxygen flow 3 L/min) to establish peripheral venous access. 1. Assess the difficulty of palpating the spinous process (1 degree: easy - slight or moderate pressure on the tissue; Grade 2: moderately significant tissue compression; 3 degrees: Difficult/unable to palpate). 2. If the patient could not cooperate due to hip pain, iliofascial space block (20mL, 0.4% ropivacaine) was performed in the supine position, and 15min later, the patient lay on his side (affected side up).

In the US-AS group, the intraspinal structure was evaluated using a portable ultrasonic system (Sonosite, low frequency convex array probe 2-5 MHz) (ultrasonic prescan to determine the best intervertebral space, best puncture Angle and best puncture depth). The measurement methods (in-plane measurement of paracentral transverse section (LTP), out-of-plane measurement of paracentral sagittal section (LSC) and in-plane measurement

of paracentral sagittal section (IPP)) were recorded, and the optimal puncture section considered by the operator (the widest acoustic window at the back of the complex) was selected to record the best gap, puncture Angle and depth. In the sterile state, traditional blind operation was performed; The positioning time, the depth and width of the retrodural complex, the first successful attempt (first skin piercing without redirection), the number of skin piercings, the number of redirects, and the operation time (probe touching the skin until the end of the operation) were recorded. After successful epidural puncture, 25G lumbar anesthesia needle was inserted (if CSF outflow was not smooth, the epidural needle could be rotated in place and then re-inserted into the epidural puncture). Subarachnoid block (2.5mL/12.5mg of 0.5% ropivacaine without high glucose) was performed immediately after CSF outflow was smooth, followed by epidural catheter. If there is no CSF after withdrawal, skin puncture should be performed again. The maximum number of skin puncture should be 6 times, and the cumulative redirection of each skin puncture should not exceed 6 times. If six skin piercings are unsuccessful, traditional palpation, replacement of puncture Spaces, or general anesthesia are considered and recorded.

In the US-RTG group, the optimal puncture section considered by the operator was selected and recorded directly in the plane of the paracentral transverse section, out of the plane of the paracentral sagittal section or in the plane of the paracentral sagittal section for real-time ultrasound guided lumbar epidural anesthesia. The positioning time, the depth and width of the retrodural complex, the first successful attempt (first skin piercing without redirection), the number of skin piercings, the number of redirects, and the operation time (probe touching the skin until the end of the operation) were recorded. After successful epidural puncture, 25G lumbar anesthesia needle was inserted (if CSF outflow was not smooth, the epidural needle could be rotated in place and then re-inserted into the epidural puncture). Subarachnoid block (2.5mL/12.5mg of 0.5% ropivacaine without high glucose) was performed immediately after CSF outflow was smooth, followed by epidural catheter. If there is no CSF after withdrawal, skin puncture should be performed again.

The maximum number of skin puncture should be 6 times, and the cumulative redirection of each skin puncture should not exceed 6 times. If six skin piercings are unsuccessful, traditional palpation, replacement of puncture Spaces, or general anesthesia are considered and recorded.

Whether the patient was in the left or right decubitus position, the operator used the puncture needle manually and the ultrasound probe non-manually. Adverse reactions and complications were recorded in both groups, including radicular pain, bloody cerebrospinal fluid puncture, headache after dural puncture, paresthesia, back pain, whether traditional palpation was used, the puncture space was changed, or general anesthesia was used. Patient satisfaction score: Patients were asked to use a 5-point numerical rating scale to evaluate their satisfaction (1, very dissatisfied; 5, very satisfied). The VNRS, verbal numerical rating scale (0-10) and whether to add analgesic drugs were recorded in the two groups.

3. Outcomes

Primary outcomes: first attempt success rate (first skin piercing, no redirection);

Secondary outcomes: operation time (seconds), positioning time, depth and width of posterior dural complex, skin puncture number, redirection number;

Patient satisfaction score: Patients were asked to use a 5-point numerical rating scale to evaluate their satisfaction (1, very dissatisfied; 5, very satisfied).

Operation difficulty score: After the operation, the anesthesiologist will score the difficulty of this operation (1, very dissatisfied; 5, very satisfied). Change of anesthesia method (traditional blind method, USAS or USRTG, change of puncture space, general anesthesia).

Adverse reactions and complications: include radicular pain, bleeding, puncture, headache after dural puncture, paraesthesia, and back pain.

Reference

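### The envelope is opened at room entry, so palpability grading, the hip-pain block decision and lateral positioning all happen with the arm known, although none of them needs it

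*Protocol*

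**What the plan says.** The protocol settles eligibility, consent and baseline data at a visit on the day before surgery (section 4, item 1). Allocation comes from a computer-generated list and is held in "sequentially numbered and sealed opaque envelopes that can only be opened by the attending anesthesiologist when the patient enters the operating room" (section 4, item 2). On blinding, the same paragraph says of patients "Patients know nothing about grouping" and of staff "Neither the intraoperative parameter collector nor the anesthesiologist performing the procedure can blind the groups".

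The next paragraph gives the order of events in the room. It begins "When the patient enters the room, connect the monitor" and goes on to oxygen and venous access. The first numbered step is "Assess the difficulty of palpating the spinous process", on a three-level scale. The second is conditional: "If the patient could not cooperate due to hip pain, iliofascial space block (20mL, 0.4% ropivacaine) was performed in the supine position", followed by a 15-minute wait and turning the patient on the side. The US-AS and US-RTG procedures are described only after this.

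The primary outcome (section 4, item 3) is success at the first skin piercing with no redirection. The sample size section (3.1.1) plans 43 per arm and raises this to 48 with the words "Taking into account 10% of possible patients dropping out". The visible SAP text compares categorical variables with a Pearson chi-square or Fisher exact test.

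**The concern.** None of the steps listed between room entry and the start of the assigned technique depends on the allocation, yet the arm is already known to staff when they take place. Three things are exposed.

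- **The palpability grade.** This is a subjective measure of how difficult the puncture is likely to be. A baseline difficulty measure should be taken without knowledge of the arm.
- **The hip-pain block.** The protocol gives no objective trigger and names no one to make the decision. The block is given because pain prevents cooperation, so on the protocol's own reasoning it may affect puncture conditions. One redirection turns a success into a failure, so the primary outcome is sensitive to those conditions. Block use is not among the items to be recorded, so an imbalance between arms could not be seen afterwards.
- **Losses in the interval.** A patient who cannot proceed to puncture at this stage is lost after allocation, with the arm known to staff.

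The operator cannot be blinded once the techniques diverge, but can be until then. This part of the performance and attrition bias is therefore avoidable.

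**Working it through.** **Order of events (protocol section 4, items 1 and 2)**

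| Step | Arm known to staff? | Needs the arm? |
|---|---|---|
| Eligibility, consent, baseline data (day before) | No | No |
| Room entry, envelope opened | Yes, from here | – |
| Monitor, oxygen, venous access | Yes | No |
| Palpability grade | Yes | No |
| Hip-pain block if needed, 15-minute wait | Yes | No |
| Lateral position | Yes | No |
| Assigned technique, with any preparation specific to it | Yes | Yes |

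**The plan's own figures.** Inputs from section 3.1.1 are 80.7% and 52.6%, two-sided alpha 0.05, 80% power and 10% dropout. The pooled-variance formula for two proportions, without continuity correction, is

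n = [1.960 × √(2 × 0.6665 × 0.3335) + 0.842 × √(0.807 × 0.193 + 0.526 × 0.474)]² / 0.281² = 43 per arm.

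Then 43 / 0.90 = 47.8, rounded up to 48. Both stated figures are reproduced, and the timing of the envelope does not change them. The allowance is 48 − 43 = 5 patients per arm, and the planned difference is 80.7 − 52.6 = 28.1 points.

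**Selective loss, worst case.** Assume that k patients who would have failed leave one arm after opening, that none leave the other arm, and that the lost patients are left out of the analysis. The observed rate moves from x/48 to x/(48 − k). The count x = 33 is chosen for illustration and lies between the two planned rates.

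- k = 1: 33/47 = 70.2%, a shift of 1.5 points from 68.8%
- k = 3: 33/45 = 73.3%, a shift of 4.6 points
- k = 5: 33/43 = 76.7%, a shift of 8.0 points

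With k = 5 and counts near the two planned rates, 25/48 to 25/43 is 52.1% to 58.1% (6.1 points), and 39/48 to 39/43 is 81.3% to 90.7% (9.4 points). If every patient whose envelope was opened stays in the denominator, exclusion causes no shift.

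**Unequal block use.** Bias = difference in block use between arms × effect of the block on first-attempt success. The documents give neither factor. Assuming a 10 to 30 point difference in use and a 10 to 20 point effect, the bias runs from 0.10 × 0.10 = 1 point to 0.30 × 0.20 = 6 points. The upper end needs block use of at least 30% in one arm, which nothing in the documents supports.

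**The case against.** The strongest reply is that this is a refinement of a sound procedure. Envelopes are sequential, sealed and opaque, and eligibility and consent come before opening. The wording may also be meant mainly to bar opening before room entry. That stands as far as it goes: a reader might infer that allocation concealment is broken, and it is not. But the rule still permits opening at entry, ahead of steps that do not need the arm.

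Other stronger readings also go beyond the text:

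- **That an unblinded operator decides on the block.** The sentence is passive and names no one. It is an inference, though a reasonable one, because the operator and the recorder are the only clinical roles described and both are unblinded. The documents also give no reason to expect use to differ in a particular direction.
- **That patients leave because of their arm.** Patients are blinded. The risk lies with decisions by staff.
- **That lost patients will be excluded from analysis.** The visible SAP text defines no analysis set, but part of the SAP is not in the copy reviewed, so its absence from the whole plan cannot be asserted. A change to general anesthesia is itself a listed outcome, and the 10% allowance is not tied to this interval.
- **That the block distorts the pain records.** The protocol says "The VNRS, verbal numerical rating scale (0-10) and whether to add analgesic drugs were recorded in the two groups" but not when, or which pain is scored. Neither item is in the outcomes list, and both arms receive the same subarachnoid block. Carry-over is speculative.

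The block matters only for patients with hip pain, and enrolment is not limited to hip fracture. Finally, US-AS has a prescan before the sterile puncture whereas US-RTG goes directly to guided needling. Sterile preparation relative to first probe contact may therefore differ by arm, so the envelope must be opened before any such preparation.

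**Conclusion.** The point holds as an avoidable weakness in the timing of the envelope. A subjective baseline grade, a discretionary co-intervention and any losses before puncture fall after allocation, among staff who know the arm, and nothing in the listed steps requires this. It is a matter of performance and attrition bias after allocation.

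The size and direction of any bias are unknown. The 8.0-point shift should not be read as an expected bias: it needs the full allowance of 5 to fall in this interval, in one arm only, all would-be failures, and all excluded from analysis. The 1 to 6 points for unequal block use is a product of two assumed ranges. The conclusion rests on the stated order of events and the stated lack of staff blinding, not on these figures. The change is worth making because it costs little.

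**What to change.** Amend section 4, item 2 along these lines: *The envelope is opened after palpability grading, after any hip-pain block and its waiting period, and after lateral positioning, immediately before the first step that differs between arms, including any arm-specific sterile preparation or probe contact. Consented patients who do not reach this point are not randomised and are entered in a log with the reason; the envelope passes to the next patient.*

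In addition:

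- Record hip-block use (yes or no) for every patient and report it by arm.
- State in the SAP that every patient whose envelope was opened is analysed in the assigned arm, if it does not already say so.

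The clinical criterion for the block, and who applies it, are for the investigators to specify.

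The cost is a short amendment, one field on the record form and a simple log. The team learns the arm a few minutes later (longer when a block is given), so equipment for both techniques must be ready. Operation time runs from probe contact, so its definition is unaffected, and the sample size stays at 48 per arm. For patients already randomised, report losses after opening by arm, and block use by arm where it can be retrieved.
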